Study treatment should be administered by the patient once per day. Following enrollment (Visit 3/Day 1) patients will return to the site at 2 week intervals until Visit 5 (Month 1). Thereafter, scheduled visits will be monthly (please refer Table 7-1 for study visit evaluation schedule). Patients may return to the study center more frequently at the physician's discretion as clinically indicated or as per standard of care. Serious adverse events (SAEs) will be reported to the Novartis safety database within 24 hours of investigator or treating physician's knowledge of the event from the time the patient has signed informed consent until at least 30 days after the patient stopped study treatment. All other assessments are performed as per standard of care at the site and will not be captured in the eCRF.

Patients who discontinue study treatment before completing the study should be scheduled for a visit within 7 days after the last dose, at which time all of the assessments listed for the end of treatment (EOT) visit (i.e. Month 24). The planned duration of treatment in this study is for a maximum of 24 months.

[figure not shown]

Figure 4-1 Study design

DT = Dispensible tablet FCT = Film-coated tablet EOT = End of treatment

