6.3.1.2 Elevations in serum creatinine

Serum creatinine should be monitored during the study as stated in the visit evaluation schedule in Table 7-1.

In case of a single increase in serum creatinine, the assessment will be repeated at the next visit, or as clinically indicated.

A deferasirox dose reduction of 7 mg/kg/day for the FCT should be performed if there is a rise in serum creatinine of 33% above Baseline value (average of Visit 1 and 2) resulting in a serum creatinine above the ULN on 2 consecutive visits (a minimum of 7 days apart).

If after a dose reduction, a progressive increase in serum creatinine beyond the ULN is observed, a treatment interruption is recommended.

After a treatment interruption, if serum creatinine falls below the age appropriate ULN on 2 consecutive visits, it is recommended to resume therapy at 50% of the last dose, and after 1 month, if the serum creatinine increase does not recur, study medication can be returned to 100% of the last dose (including body weight adjustment if required).

Use of deferasirox is contraindicated in patients with estimated creatinine clearance less than 60 mL/min.

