6.3.2 Follow-up for toxicities

Patients whose treatment is interrupted or permanently discontinued due to an AE or abnormal laboratory value must be followed at least once a week for 4 weeks, and subsequently at 4 week intervals, until resolution or stabilization of the event, whichever comes first.

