10.5.2.2 Laboratory abnormalities

All laboratory values will be converted into SI units and the severity grade calculated using the low/normal/high classifications based on laboratory normal ranges, and for selected parameters by notable/extended ranges (see Table 10-1 below).

The following summaries will be generated separately for hematology, biochemistry and urinary laboratory tests:

- shift tables using normal/notable/extended ranges to compare Baseline to the worst on-treatment value
- listing of all laboratory data with values flagged to show the corresponding normal/notable/extended ranges

Laboratory values (and changes from Baseline) will be summarized by descriptive statistics (n, mean, standard deviation, minimum, lower quartile, median, upper quartile and maximum) by scheduled visits.

Table 10-1 Definition of notable/extended ranges for laboratory tests

Laboratory test

Criteria for notable ranges

Novartis	Confidential	Page 58
Amended Protocol Version 01 (Clean)		Protocol No. CICL 670AIC04

Laboratory test	Criteria for notable ranges
Platelet count	< 100 × 10 ⁹ /L (extended range < 50 × 10 ⁹ /L)
Absolute neutrophils	$< 1.5 \times 10^{9}$ /L (extended range $< 0.5 \times 10^{9}$ /L)
Serum creatinine	> 33% increase from Baseline and > ULN at 2 consecutive measurements at least 7 days apart
Creatinine clearance	< 60 mL/min at 2 consecutive measurements at least 7 days apart (extended range < 40 mL/min at 2 consecutive measurements at least 7 days apart)
Urinary protein/urinary creatinine ratio	> 1.0 (mg/mg) at 2 consecutive measurements at least 7 days apart
ALT/SGPT and AST/ SGOT	> 5 × ULN and 2 × Baseline (extended range > 10 × ULN and > 2 × Baseline value)

ULN = Upper limit of normal range; ALT/SGPT = alanine aminotransferase/ serum glutamic pyruvic transaminase; AST/SGOT = Aspartate aminotransferase/serum glutamic oxaloacetic transaminase

Creatinine clearance will be estimated using the Cockcroft-Gault equation and the Schwartz formula (for pediatric population) and will be displayed using relative change from baseline by categories.

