2.3.3.2 Laboratory data and vital signs

Laboratory data (biochemistry, hematology, and urinary parameters as well as serum creatinine, creatinine clearance, and proteinuria) and vital signs will be collected at screening visits, regular patient visits, and EOT.

If two or more assessments are performed within a time window then the assessment closest to the planned visit will be used in analyses by time window. When two values are equidistant from the planned assessment, the later one will be used in analyses.

Note: For worst post-baseline assessment, all on-treatment values are considered regardless of time windows. Table 2-2 shows the defined time windows, where a month is regarded as 4 weeks.

Table 2-2 Time windows for laboratory and vital signs data

Time window	Planned visit timing	Time window definition
On-treatment		
Baseline	On or before Study Day 1*	≤ Study Day 1*
Week 2	Study Day 15	Study Day 2 to Study Day 21
Month 1	Study Day 29	Study Day 22 to Study Day 43
Month 2	Study Day 57	Study Day 44 to Study Day 71
Month 3	Study Day 85	Study Day 72 to Study Day 99
Month 4	Study Day 113	Study Day 100 to Study Day 127
Month 5	Study Day 141	Study Day 128 to Study Day 155
Month 6	Study Day 169	Study Day 156 to Study Day 183
Month 7	Study Day 197	Study Day 184 to Study Day 211
Month 8	Study Day 225	Study Day 212 to Study Day 239
Month 9	Study Day 253	Study Day 240 to Study Day 267

Time window	Planned visit timing	Time window definition
Month 10	Study Day 281	Study Day 268 to Study Day 295
Month 11	Study Day 309	Study Day 296 to Study Day 323
Month 12	Study Day 337	Study Day 324 to Study Day 351
Month 13	Study Day 365	Study Day 352 to Study Day 379
Month 14	Study Day 393	Study Day 380 to Study Day 407
Month 15	Study Day 421	Study Day 408 to Study Day 435
Month 16	Study Day 449	Study Day 436 to Study Day 463
Month 17	Study Day 477	Study Day 464 to Study Day 491
Month 18	Study Day 505	Study Day 492 to Study Day 519
Month 19	Study Day 533	Study Day 520 to Study Day 547
Month 20	Study Day 561	Study Day 548 to Study Day 575
Month 21	Study Day 589	Study Day 576 to Study Day 603
Month 22	Study Day 617	Study Day 604 to Study Day 631
Month 23	Study Day 645	Study Day 632 to Study Day 659
Month 24	Study Day 673	Study Day 660 to Study Day 687
Month 25	Study Day 701	Study Day 688 to Study Day 715
Month 26	Study Day 729	Study Day 716 to Study Day 743
Month 27	Study Day 757	Study Day 744 to Study Day 771
Month 28	Study Day 785	≥ Study Day 772
EOT		

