2.9.3 Laboratory data

Hematology, serum chemistry, and urinalysis parameters will be presented using standard international (SI) units and the severity grade calculated using the low/normal/high classifications based on laboratory normal ranges, and for selected parameters by notable/extended ranges.

Raw values as well as absolute and relative change from baseline values for hematology, biochemistry, and urinalysis laboratory parameters will be summarized descriptively by visit (see Table 2-2 for time windows definition).

The following summaries will be generated separately for hematology, biochemistry, and urinary laboratory tests:

- shift tables using normal/notable/extended ranges to compare baseline to the worst ontreatment value
- listing of all laboratory data with values flagged to show the corresponding normal/notable/extended ranges

All data, including data from unscheduled visits, will be considered when identifying abnormal values.

Shift tables based on normal ranges to compare baseline to the worst post-baseline value will be provided by parameter for hematology, biochemistry, and urinary laboratory data.

A similar shift table will be provided based on notable/extended ranges for key safety laboratory parameters defined in Section 10.5.2.2 (Clinical Trial Protocol CICL670AIC04 Amended Protocol Version 1, 25 October 2017).

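### Read literally, the two-measurement criteria in Protocol Table 10-1 do not flag a sustained renal abnormality whose retests are all less than 7 days apart

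*Protocol*

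**What the plan says.** Protocol 10.5.2.2, Table 10-1, sets the notable range for serum creatinine as "> 33% increase from Baseline and > ULN at 2 consecutive measurements at least 7 days apart" and for creatinine clearance as "< 60 mL/min at 2 consecutive measurements at least 7 days apart". The extended clearance range (below 40 mL/min) and the urine protein/creatinine row (above 1.0 mg/mg) use the same condition of two consecutive measurements and a 7-day minimum.

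SAP 2.9.3 adopts these ranges without redefining them: "A similar shift table will be provided based on notable/extended ranges for key safety laboratory parameters defined in Section 10.5.2.2". It adds: "All data, including data from unscheduled visits, will be considered when identifying abnormal values". SAP 2.3.3.2 does not reduce the data to one value per visit window either: "For worst post-baseline assessment, all on-treatment values are considered regardless of time windows".

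Three provisions allow tests outside the schedule:

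- Protocol 6.3.1.2: "In case of a single increase in serum creatinine, the assessment will be repeated at the next visit, or as clinically indicated".
- Protocol 4.1: "Patients may return to the study center more frequently", at the physician's discretion.
- Protocol 6.3.2: after an interruption or discontinuation for an adverse event or abnormal laboratory value, patients "must be followed at least once a week for 4 weeks, and subsequently at 4 week intervals".

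**The concern.** The two-measurement condition is evidently there to separate a sustained abnormality from a single stray value. With all values kept, the wording can do the reverse: an additional abnormal result between two others, which strengthens the evidence, removes the flag. Whether a patient is counted then depends partly on how often the site retested, and not only on what the kidney function did.

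What is at stake is the count of patients with confirmed notable or extended values in the shift table and the matching listing flags. The SAP plans at most 58 patients, so each missed patient is worth at least 1/58 = 1.7 percentage points.

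**Working it through.** The plan gives no figure to reproduce, so the check applies the rule to sets of measurement days.

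**Rules compared**

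- Literal rule, from Table 10-1 with all values kept (SAP 2.9.3): flagged if some adjacent pair is abnormal at both t(i) and t(i+1), with t(i+1) − t(i) ≥ 7 days.
- Run rule, for comparison: flagged if two abnormal values are at least 7 days apart and every value between them is abnormal.

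If every gap between abnormal values is under 7 days, no adjacent pair can satisfy the literal rule, whatever the total span.

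**Smallest example.** Take abnormal values on Days 100, 104, 108 and 112. The gaps are 4, 4 and 4 days and the span is 112 − 100 = 12 days. The literal rule does not flag this. Delete Days 104 and 108, and the remaining gap of 12 days is flagged.

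**Regular retests.** Assumed, not in the documents: the abnormality is first seen at Month 2 (Day 57) and lasts 5, 7, 10, 14, 21, 27, 28, 35 or 56 days. Retests run at a fixed interval until the first normal value, on top of the 28-day visits.

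| Retest interval | Literal rule flags | Run rule flags |
|---|---|---|
| 2, 3, 4 or 5 days | none | 10 days and longer |
| 6 days | none | 14 days and longer |
| 7 days | 7 days and longer | 7 days and longer |
| 10 days | 10 days and longer | 10 days and longer |
| 14 days | 14 days and longer | 14 days and longer |
| scheduled visits only | 28 days and longer | 28 days and longer |

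A 28-day elevation is therefore flagged with weekly or monthly tests and missed with tests every 2 to 6 days.

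**Close retesting that stops.** Take retests 3 days apart on Days 60, 63 and 66, then the Month 3 visit on Day 85. If the value is still abnormal on Day 85, the pair Day 66 and Day 85 (gap 19) is flagged. If the value was abnormal through Day 66 but normal by Day 85, the patient is never flagged, although the abnormal run spans 66 − 57 = 9 days.

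**Scheduled visits alone.** Protocol 7.1 allows ±7 days. From Month 1 the smallest gap is 28 − 14 = 14 days, so from there the problem comes only from unscheduled or follow-up tests. Between Week 2 and Month 1 the nominal gap is 14 days, so the allowance alone could bring it under 7.

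**Irregular retests.** This simulation used 20,000 episodes per setting. Assumed: duration is 7 days plus an exponential, mean 14 days in total, with retests until normal. Among episodes that meet the run rule, the literal rule also flags:

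- about 41% with gaps of 2 to 7 days;
- about 76% with gaps of 2 to 10 days;
- about 91% with gaps of 5 to 9 days.

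The answer moves with the assumed gap, which the documents do not supply.

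**The case against.** Several points on the other side carry weight.

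- **Primary objective.** A reader might infer that renal events drop out of the primary safety result. The documents do not support that. SAP 2.6.1 and 2.6.2 analyse creatinine and clearance as changes from baseline, while Table 10-1 sits under other safety objectives.
- **Patients remain visible.** SAP 2.9.3 also plans normal-range shift tables on the worst value, with no confirmation needed, and a listing of all laboratory data. Under Protocol 8.1.1, abnormalities that are clinically significant or change study medication are adverse events.
- **Follow-up after interruption.** A reader might infer that weekly follow-up leaves only gaps of exactly 7 days able to qualify. That is too strong. One test in each calendar week can give gaps above 7 days, Protocol 6.3.2 does not specify a creatinine sample each time, and the intervals lengthen after 4 weeks.
- **Order of events.** Protocol 6.3.1.2 ties its dose reduction to two visits at least 7 days apart, with interruption coming later. A patient interrupted by that route has normally already produced a near-qualifying pair. It is only near: that rule uses the average of Visits 1 and 2 as baseline, unscheduled values may fall between the visits, and patients interrupted for another reason are not covered.
- **Intent.** A programmer may already read the criterion as an abnormality confirmed at least 7 days later, which would remove the problem. Neither document says so, and two programmers could report different counts from the same data.

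These limit the consequence. They do not remove the ambiguity.

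**Conclusion.** The point holds as a defect in one analysis definition. Under the literal wording with all values kept, a patient whose abnormal values are all less than 7 days apart is not flagged, whatever the duration. This applies to serum creatinine, both creatinine-clearance ranges and the urine protein/creatinine ratio. The undercount is confined to the notable/extended shift table and the listing flags, and it depends on retest intensity.

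Its size is unknown and could be zero. Zero detection at fixed gaps of 2 to 6 days is arithmetic, and the simulated percentages illustrate assumed retest patterns; neither estimates what happens in this trial. A patient with any earlier or later qualifying pair is still counted. There is one arm and no hypothesis test, so no comparison is biased. The correction is worth making because it costs little and fixes one meaning for the reported counts.

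**What to change.** In SAP 2.9.3, add one definition for serum creatinine, creatinine clearance (notable and extended) and urine protein/creatinine ratio: the Table 10-1 criterion is met when two measurements at least 7 days apart both meet it and every measurement in between also meets it. Note it in SAP Section 4 as a clarification of the protocol table.

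Every pair that the literal rule counts still counts, because an adjacent pair has nothing in between. The change does not remove all dependence on test timing: a 10-day elevation retested every 6 days still shows a span of only 6 days and is not counted.

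This is an analysis definition and alters no dose-modification or other clinical action rule. Protocol 6.3.1.2 speaks of visits where Table 10-1 speaks of measurements; the sponsor should state whether the two are meant to correspond.

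The cost is a small programming change, and the reported counts of notable values may rise slightly.

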6.3.1.4 Changes in urine protein/creatinine ratio

Proteinuria should be monitored during the study as stated in the visit evaluation schedule in Table 7-1.

For patients who develop proteinuria or a worsening of pre-existing proteinuria (assessed by a dipstick) at any visit, urine samples should be collected and assessed by the local laboratory.

In case of a single increase of the urinary protein/creatinine ratio the assessment should be repeated at the next visit.

Deferasirox dose reduction by 50% should be performed if the urinary protein/creatinine ratio increases to > 0.5 (mg/mg) in 2 consecutive second-void urine samples (a minimum of 48 hours apart), if all other causes of proteinuria have been excluded.

Deferasirox must be temporarily interrupted if the urinary protein/creatinine ratio increases to > 1.0 (mg/mg) in 2 consecutive second-void urine samples (a minimum of 48 hours apart).

Should proteinuria persist, study treatment may be discontinued if the investigator believes it is in the best interest of the patient. Novartis may be contacted by the investigator to discuss dosing options if the investigator so desires.

Dose adjustment will be based on local laboratory results.

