7.1 Study flow and visit schedule

Table 7-1 lists all of the assessments and indicates with an "X", the visits when they are performed.

Patients should be seen for all visits to perform the scheduled assessments on the designated day, or as close to is as possible, i.e., not exceeding \pm 7 days. In this clinical trial, a week is 7 calendar days. Visits should be planned respective to Visit 3, rather than in relation to the previous visits.

All data obtained from these assessments must be supported in each patient's source documentation. No eCRF will be used as a source document. The table indicates which data are entered into the database (D) or remain in source documents only (S) (column category).

Table 7-1 Visit evaluation schedule

	Category	Protocol section	Screening	(z visits > 1week apart)¹							Tr	eatme	ent Pe	riod						End of Treatment	Safety Follow- up
Visit no.			1	2	3	4	5	6	7	8	9	10	11	12	13	14	15	16	17 to 27	28²	
Study month			-2	2W	D1	W2	M1	M2	М3	M4	М5	М6	М7	M8	M9	M10	M11	M12	M13 to M23	M24 or Within 7 days of last dose	30 days after last dose
Informed consent	(D)	7.1.1	Х																		
Inclusion/ exclusion criteria	(D)	7.1.1.1	Χ	Х																	
History of disease	(D)	7.1.1.3	Χ																		
Demography	(D)	7.1.1.3	Χ																		
Relevant medical history/current medical conditions	(D)	7.1.1.3	X																		
Prior chelation therapy	(D)	7.1.1.3	Х																		
Transfusion/RBC History	(D)	7.1.1.3	Х																		
Transfusions received	(D)	7.1.3	Х		Х	Х	Х	Х	Х	Х	Х	Х	Х	Х	Х	Х	Χ	Χ	Х	Х	
Physical exam	(S)	7.2.2.1	Х		Х	Χ	Х	Х	Х	Х	Х	Х	Х	Х	Х	Χ	Χ	Χ		Х	
Weight ³	(D)	7.2.2.3	Х		Χ	Χ	Х	Χ	Χ	Х	Х	Х	Х	Χ	Χ	Χ	Χ	Χ	Χ	Х	
Height	(D)	7.2.2.3	Х																		
Vital signs	(D)	7.2.2.2	Х	Х	Χ	Х	Х	Х	Х	Х	Х	Х	Х	Χ	Χ	Χ	Χ	Χ	Χ	Х	
Ocular exam⁴	(D)	7.2.2.4	Х															Χ		Х	
Audiometry ⁴	(D)	7.2.2.4	Х															Χ		Х	
ECG	(D)	7.2.2.7.1	Х															Х		Х	
Chest X-ray (if clinically indicated) ⁵	(D)	7.2.2.6	Х																		

	Category	Protocol section	Screening	apart)¹							Tı	eatme	ent Pe	riod						End of Treatment	Safety Follow- up
Visit no.		_	1	2	3	4	5	6	7	8	9	10	11	12	13	14	15	16	17 to 27	28 ²	
Study month			-2	2W	D1	W2	M1	M2	М3	M4	M5	М6	М7	M8	М9	M10	M11	M12	M13 to M23	M24 or Within 7 days of last dose	30 days after last dose
Prior and Concomitant medications	(D)	6.4	Х	х	х	х	Х	Х	Х	Х	Х	Х	Х	Х	Х	Х	х	Х	Х	Х	
Adverse events	(D)	7.2.2	Х	Х	Х	Χ	Х	Х	Х	Х	Х	Х	Х	Х	X	Χ	Х	Х	Х	Х	Х
Laboratory assessments ⁶ -Blood																					

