7.1.3 Treatment period

The duration of study treatment in the current study is for a maximum of 24 months.

Treatment visits will commence at Visit 3 (Baseline). Patients will return to the site at 2 week intervals until Visit 5 (Month 1). Thereafter, scheduled visits will be monthly until EOT (Visit 28/Month 24).

Having completed the 24 weeks of CICL670F2201, patients recruited at Region Europe participating sites will be invited to continue FCT or switch from DT to the FCT formulation. Patients who completed CICL670F2201 but had switched to commercially available DT or other iron chelation will still be enrolled in the current study and receive FCT after a washout period.

All patients randomized in the DT arm in CICL670F2201 and well-managed on treatment with deferasirox DT will use an equivalent FCT dose. Patient switching from DT will use an equivalent FCT dose at the start of this study corresponding to their DT dose at the end of CICL670F2201 (see Appendix 14.2). A patient who is receiving an adjusted dose at the time of completing CICL670F2201 will commence this study receiving that adjusted dose until a time when it is deemed necessary to adjust the dose by the Investigator. Patients completing CICL670F2201 that had switched to commercially available DT or other ICT will have to undergo a 5-day washout period and then use an equivalent FCT starting dose corresponding to their pre-washout iron chelator dose.

Daily dose is calculated by the physician based on the patient's actual body weight.

For details on study design and dose adjustments, see Section 4 and Section 6.3. For details of assessments, see Table 7-1.

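### The notable-range table for urine protein/creatinine ratio misses values above 1.0 mg/mg that are confirmed 2 to 6 days apart and then fall on interruption

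*Protocol*

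**What the plan says.** **Reporting rule.** Table 10-1 in Protocol 10.5.2.2 defines the notable range for this ratio as "> 1.0 (mg/mg) at 2 consecutive measurements at least 7 days apart". It gives no extended range for it. SAP 2.9.3 takes over the table: "A similar shift table will be provided based on notable/extended ranges for key safety laboratory parameters", with the definitions left to Protocol 10.5.2.2. The SAP also uses these ranges to flag values in the laboratory listing, and it includes unscheduled values when looking for abnormalities.

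**Action rule.** Protocol 6.3.1.4 states: "Deferasirox must be temporarily interrupted if the urinary protein/creatinine ratio increases to > 1.0 (mg/mg) in 2 consecutive second-void urine samples". The two samples must be at least 48 hours apart. A lower step also exists: "Deferasirox dose reduction by 50% should be performed if the urinary protein/creatinine ratio increases to > 0.5 (mg/mg" on two samples with the same 48-hour spacing, but only when other causes of proteinuria have been ruled out.

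**Timing of repeats.** The same section sets the default: "In case of a single increase of the urinary protein/creatinine ratio the assessment should be repeated at the next visit". On visits, Protocol 7.1.3 says: "Patients will return to the site at 2 week intervals until Visit 5 (Month 1). Thereafter, scheduled visits will be monthly". Protocol 7.1 allows 7 days either side and adds: "Visits should be planned respective to Visit 3, rather than in relation to the previous visits". After an interruption for an adverse event or laboratory value, Protocol 6.3.2 asks for follow-up at least weekly for 4 weeks.

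**The concern.** The same ratio and the same threshold carry two confirmation intervals: 48 hours for acting and 7 days for reporting. Serum creatinine shows the alignment that is missing here, since its dose rule (Protocol 6.3.1.2) and its Table 10-1 row both use 7 days.

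When the confirming sample comes early, the drug is interrupted before the 7-day condition can be met. Whether the patient is counted then depends on the ratio staying above 1.0 after the action that the protocol itself requires. Proteinuria that reverses off drug is the pattern that drops out. Overall safety is the primary objective, so a laboratory table should not depend on how soon a site happened to repeat the sample.

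**Working it through.** The plan states no figure on this point, so there is none to reproduce. The check applies both rules to sample sequences, and then asks how often the scheduled visits could produce a short gap.

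**Step 1. The rules**

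- Interruption trigger: two consecutive values above 1.0, gap at least 2 days (Protocol 6.3.1.4).
- Notable range: two consecutive values above 1.0, gap at least 7 days (Table 10-1).

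**Step 2. Sequences.** The first two values are 1.3, separated by the gap shown. The third value comes 7 days after the second and is either 0.3 (recovered) or 1.2 (still raised).

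| Gap, first to second value | Third value | Interruption trigger met | Notable range met |
|---|---|---|---|
| 2, 3, 4, 5 or 6 days | recovered | yes | **no** |
| 2, 3, 4, 5 or 6 days | still above 1.0 | yes | yes |
| 7, 10, 14 or 28 days | recovered | yes | yes |
| 7, 10, 14 or 28 days | still above 1.0 | yes | yes |

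The two rules disagree only in the first row.

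**Step 3. Persistent values sampled closely.** Take values above 1.0 on Days 0, 2 and 8. The consecutive gaps are 2 − 0 = 2 and 8 − 2 = 6 days. Read literally, neither pair qualifies, although the ratio has been raised over 8 days. A 6-day gap is compatible with at-least-weekly follow-up. If the rule were instead read as an unbroken run above 1.0 spanning at least 7 days, the case would be flagged. The SAP does not say which reading applies.

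**Step 4. Gaps between scheduled visits.** Planned days are from SAP Table 2-2 (1, 15, 29, 57, 85 and so on). The window is 7 days either side, counted from Visit 3.

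| Visits | Nominal gap (days) | Smallest gap allowed (days) |
|---|---|---|
| 3 to 4 | 15 − 1 = 14 | (15 − 7) − 1 = 7 |
| 4 to 5 | 29 − 15 = 14 | (29 − 7) − (15 + 7) = 0 |
| 5 to 6, and later monthly pairs | 57 − 29 = 28 | (57 − 7) − (29 + 7) = 14 |

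A repeat at the next scheduled visit therefore nearly always satisfies the 7-day rule. Short gaps come from unscheduled repeats or a compressed Visit 4 to 5 interval. An end-of-treatment visit brought forward by early discontinuation could also produce one.

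**Step 5. Size.** Leaving aside the Step 3 cases, among patients who meet the interruption trigger:

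share missing = P(confirming gap under 7 days) × P(ratio at or below 1.0 at the next sample)

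The documents give neither term. Assuming 30% to 80% recovery:

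- 10% early repeats (assumed): 0.10 × 0.30 = 3% to 0.10 × 0.80 = 8%.
- 25% early repeats (assumed): 0.25 × 0.30 = 7.5% to 0.25 × 0.80 = 20%.

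For scale, take the SAP's planned maximum of 58 patients and Clopper-Pearson 95% intervals. One missed case is 1/58 = 1.7% (0.0 to 9.2) and three are 3/58 = 5.2% (1.1 to 14.4). If these were the only cases, the notable row would read 0/58 (0 to 6.2). The counts of one and three are assumptions.

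**The case against.** The strongest reply has four parts.

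1. **The default repeat is the next visit.** Forty-eight hours is a minimum spacing, not a schedule. This stands, and it limits the point to short gaps.
2. **The patients are captured elsewhere.** Under Protocol 8.1.2.1, a laboratory abnormality for which the protocol requires a dose hold is an adverse event. It should enter the treatment-emergent tables, including the one for events needing dose adjustment or interruption (SAP 2.9.1). Interruptions are summarised with reasons (SAP 2.5.1). SAP 2.9.3 also plans a normal-range shift to the worst value with no 7-day condition, which would help if the ratio has a laboratory normal range. This also stands. However, none of these outputs counts patients whose measured ratios met the trigger, and the adverse event route depends on investigator reporting and coding.
3. **A reporting threshold may be stricter than an action threshold.** Table 10-1 uses 7 days for creatinine, creatinine clearance and this ratio alike. That is a legitimate choice, but the plan does not give it as the reason, and a second row would keep the uniform rule intact.
4. **The Day 0, 2 and 8 sequence is unusual.** It is. One more value above 1.0 taken at least 7 days after the preceding sample would flag the patient.

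A reader might go further and infer that every case recovering on interruption disappears from safety reporting, or that 30% to 80% of interruptions would be missing if 30% to 80% of patients recover. The documents support neither. Cases confirmed at consecutive scheduled visits are normally counted despite later recovery. The second inference treats the recovery rate as the missing share, which is true only if every confirming sample is taken within 7 days.

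**Conclusion.** The mismatch is real and its effect is limited. The notable-range shift table and its listing flags omit patients whose two consecutive ratios above 1.0 are 2 to 6 days apart and whose ratio then falls on interruption. On a literal reading they also omit persistent cases whose consecutive samples are all under 7 days apart. Safety reporting as a whole does not lose these patients, provided the adverse event and dosing records are completed as the protocol requires. The ratio is not among the primary laboratory variables in SAP 2.6.1.

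The size cannot be determined from the documents; the percentages above rest on assumed rates of early repeat and recovery. This is a minor reporting point that is cheap to correct.

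A reader might also call the missing category above 0.5 a defect of the same kind. Nothing in Table 10-1 commits it to mirror every dosing trigger. A laboratory-only row could not apply the condition that other causes be excluded, so it would not by itself reproduce the dose-reduction rule.

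**What to change.** Reconcile Protocol 6.3.1.4 and Table 10-1 for reporting purposes, without altering any clinical rule:

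- In the SAP 2.9.3 notable-range output, add the number and percentage of patients with a ratio above 1.0 mg/mg on two consecutive on-treatment samples at least 48 hours apart, unscheduled samples included.
- Keep the existing 7-day criterion as a separate row labelled persistent. State whether it requires an adjacent pair 7 days apart or an unbroken run above 1.0 spanning 7 days.
- Apply the matching flags in the laboratory listing.
- A row for values above 0.5 is optional. If added, label it as a laboratory finding and not as the dose-reduction trigger.

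The cost is a short SAP change and a little programming on data already collected. The downside is possibly a few more flagged patients.
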